Animal and human studies have demonstrated that moderate intensity exercise when compared to exertional exercise or strength training result in shifting of cytokine expression toward anti-inflammation and diminished markers of oxidative stress.^{7,16,24,35,45} The benefit of early exercise in AIS and sICH in decreasing pro-inflammatory factors has been demonstrated in animal models when exercise is introduced between 24 hours and three days in AIS and at three or four days in sICH.^{40,53-55} An exercise intervention that is standardized in frequency with measureable intensity and duration is necessary to explore the effects of an exercise intervention in acutely ill patients with AIS and sICH. We hypothesize that a balancing of the inflammatory response after sICH can occur with the application of moderate exercise in the acute period.

Objectives (include all primary and secondary objectives)

Primary Objective: to determine the effects of twice-daily, lower extremity CE of 20 minutes duration plus usual care, compared to usual care alone, on the trajectories of M1 versus M2 cytokine phenotypes in the serum and cerebrospinal fluid (CSF).

Secondary Objectives:

- (i) To determine the effects of twice-daily, lower extremity CE of 20 minutes duration plus usual care compared to usual care alone and a third retrospective cohort of patients receiving usual care during the COVID-19 pandemic on, the immediate and sustained physical impairment, disability scores and relevant covariates such as delirium and hospital acquired infections at NCCU discharge and 30 days after hemorrhage.
- (ii) To determine the correlation between serum and cerebrospinal fluid cytokines in patients with external CSF drainage as part of their care.
- (iii) To explore the relationship between pre-morbid physical function and quality of life and changes in inflammatory factors among all participants.
- (iv) To determine the effects of twice-daily, lower extremity CE of 20 minutes duration plus usual care alone on hemispatial neglect as measured by the Sunnybrook Neglect Assessment Procedure on day 1 of the study at transfer from the ICU or discharge from the hospital and 30 days after hemorrhage.

2. Background (briefly describe pre-clinical and clinical data, current experience with procedures, drug or device, and any other relevant information to justify the research)

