Enrollment of subjects within the original study framework was put on hold beginning on March 16, 2020 due to the necessary hospital response to prevent further spread of COVID-19 and to maximize resources to treat hospitalized patients. Adding a second control group where all variables except for biologic and survey data will allow comparison of three different care conditions, intervention plus usual care, usual care only and usual care only during a pandemic. Usual care in terms of study visit timing, number, and length may be different than pre-pandemic care paradigms due to staff redeployment and restructuring are care areas to support care during a disaster.

3. Study Procedures

- a. Study design, including the sequence and timing of study procedures (distinguish research procedures from those that are part of routine care).

This pilot study uses a randomized parallel group design to determine the difference in the expression of pro- and anti-inflammatory cytokines in response to this specific exercise intervention plus usual care versus usual care only. Patients will be enrolled on day 3 of illness and data will be collected for seven consecutive days. We seek to enroll a convenience sample of up to 100 consecutive patients with supratentorial sICH and acute ischemic stroke admitted to the Johns Hopkins Hospital Neurosciences Critical Care Unit (NCCU). Patients will be screened within 24-48 hours of arrival for eligibility according to the inclusion and exclusion criteria listed below. Informed consent will be obtained from the patient or legally authorized representative (LAR). The consenting process will be performed remotely via videoconference when possible.

Patients will be randomly assigned to the intervention plus usual care or usual care only group using a standard randomization schema generated by STATA 14.0 (College Station, Texas). The AIS and sICH cohorts will have separate randomization schemas.

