arterial line is not available the non-invasive cuff will be cycled every 5 minutes. Continuous vital signs will be extracted from the Sickbay software application, which collects physiologic data on all NCCU (see IRB00132987 Multimodality Neuromonitoring in the Neurocritical Care Unit). A clinician will observe the patient at all times during the session for signs of pain and discomfort and will administer the behavioral or visual analog pain scale every 5 minutes during the session depending on the patient's level of consciousness. Patient tolerance will be defined as the absence of the following: decline in neurological examination; sustained change in intracranial pressure, blood pressure, heart rate or oxygen saturation outside of prescribed goals per established patient specific plan of care; an increase in pain as measured by the behavioral pain scale or numeric pain rating scale not easily ameliorated by position change by the clinician; and accidental tube/device/catheter removal.^{22,34} Manual muscle strength testing using the Medical Research Council Sum Score will be performed by a clinician before the first session on days three and seven for patients in the control group. General strength will be assessed using a hand-held dynamometer for patients able to follow simple commands before the first session on days three and seven for patients in the control group. Other relevant covariates will be extracted from the medical record such as delirium screening, hospital acquired infections, volume of hematoma and cerebral edema on routine CT scans and body temperature.

The second control group, retrospective observational cohort, will consist of ischemic and hemorrhagic stroke patients admitted to the NCCU on the Johns Hopkins Hospital and Johns Hopkins Bayview campuses from March 16, 2020 through the end of the prohibition of tier II and III studies declared by the Johns Hopkins University Institutional Review Board. All data collection will be accomplished through retrospective chart abstraction. Face-to-face contact will not be required. The same clinical variables will be collected for this cohort to the extent that they are recorded in the medical record from admission to 90 days after the initial ischemic or hemorrhagic stroke.

The following samples will be obtained for the intervention + usual care group and the control group, usual care only:

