- a) A 2 teaspoon sample of the patient's serum on the day of enrollment and two additional times during the seven day study period timed with routine collection of blood, when possible, for daily blood tests while the patient is in the hospital. Blood samples will be collected from an existing arterial or central line or via venipuncture. The initial blood sample will be collected on study day 1 prior to cycling in the intervention group and between 8 am-12 pm in the control group. Subsequent samples will be drawn after the second cycling session and between 2 pm and 6 pm in the control group.
- b) A 4-5 mL sample of saliva on the day of enrollment and two additional times during the seven day study period. Saliva will be collected between 8 am-10 am in all participants and prior to the first cycling session of the day for the intervention group.
- c) A 4 mL sample of cerebrospinal fluid (CSF) on the day of enrollment and two additional times during the seven day study period timed with collection of other sampling, when an external ventricular drain is in place as a part of care. CSF sampling will occur in patients with an external ventricular drain inserted as part of their care and will end after 3 samples or when the drain is discontinued. Efforts will be made to time CSF sampling with planned sampling, if possible and sampling will be performed by a nurse or physician study team member trained in the skill as part of their job using aseptic technique. The initial CSF sample will be collected on study day 1 prior to cycling in the intervention group and between 8 am-12 pm in the control group. Subsequent samples will be drawn after the second cycling session and between 2 pm and 6 pm in the control group.

All samples will be placed on dry ice, centrifuged and stored in a -70 degree Celsius freezer within 1 hour of obtaining the sample. Samples will be labeled with de-identified data (patient study number and date only).

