If a patient meets the following stopping criteria on >2 consecutive sessions the patient will be withdrawn from the study: change in neurological examination, sustained change in intracranial pressure, blood pressure, heart rate, or oxygen saturation that is outside of provider-prescribed range, significant pain exacerbated by mobilization.^{22,34}

g. Description of what happens to participants receiving therapy when study ends or if a participant's participation in the study ends prematurely.

Upon study procedure completion participants will continue to receive usual care.

4. Inclusion/Exclusion Criteria

Inclusion criteria:	Rationale:
Age \geq 18 years	Spontaneous intracerebral hemorrhage and acute ischemic stroke is typically a disease of the adult.
Supratentorial intracerebral hemorrhage with or without intraventricular hemorrhage	Only patients with a supratentorial ICH will be included due to the fact that patients with infratentorial ICH often require surgery, introducing an overlay of inflammation above that which is caused by the ICH itself. It is known that intraventricular hemorrhage increases severity of illness and mortality, however it is a common co-occurring process in patients with ICH and should be studied concurrently. ¹³
Acute ischemic stroke with a Medical Research Council Sum Score (MRCSS) of <27.	Patients with a clinical diagnosis of stroke and motor weakness as identified by the MRCSS as less than 27. ²¹
Pre-morbid modified Rankin Score of 0-2	The modified Rankin Score (mRS) is a commonly

	used tool to quantify disability after stroke and is scored from 0 to 6 with higher scores describing increased disability including death. The mRS will be used to characterize a patient's pre-morbid functional status correlating with a patient's potential for recovery after stroke as well as an outcome measure at discharge and 30 days after hemorrhage. ^{5,13} Patients with a mRS >2 prior to admission have poor potential for recovery.
Patient must be able to provide informed consent or have a legally authorized representative to provide consent on their behalf	
Exclusion criteria:	

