a. Primary outcome variable.

Pro-inflammatory cytokines: IL-1 β , TNF α , IL-6; Anti-inflammatory/repair factors: IL-10, BDNF

b. Secondary outcome variables will be measured at discharge and 30 days post-intracerebral hemorrhage or acute ischemic stroke.

- Modified Rankin Scale (mRS)
- Barthel Index will be measured at discharge and 30 days
- Medical Research Council Sum Score and dynamometry to measure muscle strength
- Discharge location (e.g., home, nursing facility), although not well studied, is commonly associated with physical function at discharge.
- SF-12
- Vital signs (e.g., heart, rate, blood pressure, respiratory rate)
- Delirium positive days
- Hospital acquired infections (e.g., catheter associated urinary tract infection and central line associated blood stream infection)
- CSF cytokines and repair factors
- Stroke Impact Survey

c. Statistical plan including sample size justification and interim data analysis.

Sample size was calculated for a fully powered trial and 9% of this sample size will be used for this pilot according to Cocks' methodology.¹⁰ An effect size of 0.28 was used, based on a published single group observational study in critically ill patients with a primary outcome of cytokine change.⁴⁷ Detection of an effect size of 0.28 with power of 80% and an α of 0.05 requires a sample size of 400 for a full trial and 9% represents a pilot sample size of 36 participants. Due to the enrollment of two stroke phenotypes, ischemic and hemorrhagic, we will analyze each cohort separately, therefore 40 participants per cohort are required. Accounting for attrition, up to 100 participants may be consented in order to enroll up to 40 participants per cohort. Each cohort will have 20 participants in each of two arms, intervention and control. It is estimated that at least 3-5 patients will be enrolled per month over 18 months.

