Descriptive statistics will be used to report sociodemographic variables. Baseline characteristics will be compared between the two groups. If they are found to be similar, post-intervention outcomes will be compared between the groups. If the baseline characteristics are found to be different, an adjusted analysis as described below will be conducted. Mean (SD) or median (IQR) will be used to describe continuous variables, and frequency (%) will be used for categorical variables. Mean differences in cytokines between the three time points (baseline, day 3 and day 7) will be calculated for each participant in the intervention and control groups. We will also plot data over time by group. Assumptions of normality will be checked and appropriate parametric or non-parametric tests will be used to detect absolute mean differences due to the small sample size, with an a priori significance level of 0.05, although the primary aim of this study is to estimate effect size. Data quality will be ensured by analyzing all samples in duplicate and procurement of samples will be performed by the same investigator. Statistical analysis will be performed using Stata 14.0 (College Station, Texas).

Primary aim (1): To determine whether a regimen of twice daily 20-minute sessions of CE plus usual care administered to patients with sICH and AIS (n=20) increases cytokines of the M2 phenotype and decreases cytokines of the M1 phenotype within 10 days of sICH when compared to a similar group of patients with sICH receiving usual care only (n=20).

The effect size, absolute difference between the two groups and the standard error of the difference will be estimated. The standardized difference will be estimated using Cohen's d. A two-sample t-test will be used to detect differences between post-test outcomes. If the baseline outcome is different, an analysis of covariance (ANCOVA) will be used to compare the outcomes between the two groups adjusting for the baseline difference as a covariate.

Hypothesis: Patients in the CE group will demonstrate an increase in cytokines of the M2 phenotype and a decrease in the M1 phenotype when compared to the group receiving usual care only.

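### Hematoma volume is collected as a covariate but is not a prespecified model term for the sICH functional outcomes; adjustment depends on an undefined finding of baseline difference

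*Combined protocol and SAP*

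**What the plan says.** **Allocation.** Section 3a describes a standard schema generated in Stata and adds: "The AIS and sICH cohorts will have separate randomization schemas". It describes no further stratification factor, block size or minimization. Study Statistics, c gives 20 participants per arm in each cohort, analyzed separately.

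**Severity information.** Section 4, in the rationale for enrolling supratentorial hemorrhage, states: "It is known that intraventricular hemorrhage increases severity of illness and mortality". Section 3a lists among the relevant covariates to be taken from the record the "volume of hematoma and cerebral edema on routine CT scans and body temperature". It does not say which scan is meant.

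**Analysis.** Study Statistics, c compares baseline characteristics first and compares outcomes directly if they are similar. Otherwise: "If the baseline characteristics are found to be different, an adjusted analysis as described below will be conducted". What follows under the primary aim is a two-sample t-test, replaced by ANCOVA on the baseline outcome if that baseline outcome differs. No other covariate is named. Aim 2 (physical impairment and disability) is to be analyzed in the same way.

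**The concern.** The plan recognizes severity as relevant and collects a direct measure of it, but whether that measure enters the analysis depends on a look at the data with no stated criterion. Three things follow.

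- Two analysts could reach different models from the same baseline table, so the functional comparison is not fully specified.
- A prognostic variable improves precision whether or not it happens to be imbalanced. Waiting for an imbalance gives up that gain in most realizations.
- The one adjustment described does not serve every Aim 2 outcome. Table 1 schedules the Barthel Index only at ICU transfer and at 30 days, so it has no baseline value to adjust for. The Medical Research Council sum score and grip strength do have study-day-1 values.

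The stake is the quality of the effect estimate in a small pilot whose stated main purpose is to estimate effect size.

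**Working it through.** **1. The plan's own figure.** Inputs from Study Statistics, c: "Detection of an effect size of 0.28 with power of 80% and an α of 0.05 requires a sample size of 400". For two arms and a two-sided test, n per arm = 2(1.96 + 0.84)² / 0.28² = 2 × 7.84 / 0.0784 = 200, or 400 in total. Then 0.09 × 400 = 36, matching "9% represents a pilot sample size of 36 participants". The plan takes this to 40 per cohort, 20 per arm. The sample size reproduces, and nothing below changes it.

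**2. Chance imbalance in one continuous baseline marker.** At 20 per arm the SE of the standardized difference is √(2/20) = 0.316.

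- P(|difference| > 0.28) = 2[1 − Φ(0.28/0.316)] = 2[1 − Φ(0.885)] = 0.38.
- P(|difference| > 0.50) = 2[1 − Φ(1.58)] = 0.11.

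The value 0.28 is borrowed from the cytokine sample-size calculation as a yardstick. The documents give no target effect for the functional outcomes.

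**3. Would the conditional step catch it?** The criterion is not stated, so assume p < 0.05 on a baseline t-test. With 38 degrees of freedom the critical value is 2.02, so the observed difference must exceed 2.02 × 0.316 = 0.64 SD. Under randomization this happens in 5% of trials. Of the 38% with an imbalance above 0.28, about 0.05/0.38 = 13% would trigger adjustment and 87% would not. Even above 0.50, fewer than half would (0.05/0.11 ≈ 45%).

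**4. What an unadjusted imbalance does to one estimate.** The shift is the imbalance times the correlation between marker and outcome. Assume the marker explains R² = 0.20 to 0.40 of outcome variance, so the correlation is √R² = 0.45 to 0.63.

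| Imbalance (SD) | Shift at R² = 0.20 | Shift at R² = 0.40 |
|---|---|---|
| 0.28 | 0.13 SD | 0.18 SD |
| 0.50 | 0.22 SD | 0.32 SD |

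**5. Gain from a fixed covariate.** In a linear model the SE is multiplied by √(1 − R²). The cost of estimating one coefficient at N = 40 adds a factor of about √(37/36) = 1.014.

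| R² (assumed) | √(1 − R²) | With allowance | SE reduction |
|---|---|---|---|
| 0.20 | 0.894 | 0.907 | 9 to 11% |
| 0.40 | 0.775 | 0.785 | 21 to 23% |

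A simulation with 20 per arm gave SE ratios of 0.90 and 0.79. In round terms the reduction is 10 to 22%.

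Here R² means variance explained beyond whatever else is in the model. Where a baseline outcome value is also used, as it can be for muscle strength, the extra share may be smaller. The arithmetic applies to a continuous outcome in a linear model; for the modified Rankin Scale it is only a guide.

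**The case against.** The strongest reply is that this is a randomized pilot, so chance imbalance causes no bias on average. The plan also does provide for adjustment, and the size of the gain rests on an R² that no document supplies. All of that stands. It limits the point to precision and prespecification, but does not remove it: the conditional step names no criterion and no severity variable, and the data are already being collected.

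A reader might go further in four ways that the documents do not support.

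- **That severity adjustment is wholly absent.** It is not: there is a conditional step, and hematoma volume is called a relevant covariate. The gap is that no severity term is fixed in advance.
- **That the plan neglects the strongest severity markers.** The documents do not rank markers and do not call a ventricular drain one.
- **That the sICH list must be stratified by drain.** The primary objective does refer to effects "on the trajectories of M1 versus M2 cytokine phenotypes in the serum and cerebrospinal fluid (CSF", and "CSF sampling will occur in patients with an external ventricular drain inserted as part of their care", so CSF arm sizes are left to chance. But Study Statistics lists CSF cytokines as a secondary outcome, and the number of drain patients is not given. Assuming 8, 10 or 12 among 40 with fixed 20:20 arms, a split differing by four or more has a chance of 24, 27 or 30%, yet the average SE loss against an even split is only about 7, 5 or 4%. The effect detectable with 80% power is 2.4 SD at 4:4 and 2.7 SD at 2:6, so the comparison is descriptive either way. Sampling stops when a drain is removed, so stratifying would even out day-1 availability only. Enrollment had opened before the March 2020 hold, so the list would change mid-trial. A drain term changes the serum SE by under 1% once baseline cytokine is in the model (simulated, assuming 30% with drains, a 0.8 to 1.0 SD shift and a correlation of 0.6).
- **That infarct volume should be added for AIS.** The documents do not collect it, so that would be new work.

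**Conclusion.** The point holds in a limited form. For the sICH cohort's functional outcomes, a severity measure already in the data set should be a fixed model term, and the plan leaves it to a balance check with no criterion. A chance imbalance above 0.28 SD has a probability of about 38%, and most such imbalances would go unadjusted if the trigger is p < 0.05 (assumed). The expected gain is an SE about 10 to 22% lower, conditional on R² of 0.20 to 0.40 (assumed). This is an inexpensive improvement worth making. It is not a flaw that invalidates the randomized comparison, and it does not bear on the sample size.

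**What to change.** In Study Statistics, c, under the statistical plan and Aim 2, state that for the sICH cohort the randomized comparison of functional outcomes includes baseline hematoma volume as a covariate whatever the observed balance. Define it as the volume on the last routine CT before randomization, fix its scale in advance, and exclude later scans, which could be affected by the intervention. This statement would replace the balance-triggered rule for these outcomes. It does not extend to the retrospective pandemic cohort, which is not randomized.

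Cost: one model degree of freedom and a rule for picking the scan. No extra patients, procedures or measurements are needed. The change need only be made before the outcome data are analyzed.

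Optional, as a preference only: stratify sICH patients not yet randomized by presence of a drain, to even out the day-1 CSF arm sizes. If the existing list already does this, section 3a need only say so.
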